5.4.3 Cisplatin Dose Modifications – CTCAE v. 5.0

Neutropenia:

- If on the day of scheduled treatment with cisplatin the absolute neutrophil count (ANC) $<1200/\text{mm}^3$, hold the second chemotherapy treatment but not the radiation until $\text{ANC} \geq 1200/\text{mm}^3$, then treat at 100% dose.
- Neutropenic fever ($\text{ANC} < 1000/\text{mm}^3$ with a single temperature of >38.3 degrees C [101 degrees F] or a sustained temperature ≥ 38.0 degrees C for more than 1 hour) will require a 25% dose reduction of the second cisplatin dose.

Thrombocytopenia:

- If on the day of the scheduled treatment with cisplatin the platelet count is $< 75,000/\text{mm}^3$, hold the second chemotherapy treatment but not the radiation until platelets are $\geq 75,000/\text{mm}^3$ then treat at 100% dose.
- Thrombocytopenia that results in bleeding will require a 25% dose reduction of the second cisplatin dose.

Neurotoxicity:

- If Grade 2 neurotoxicity developed, hold cisplatin but continue radiation until toxicity improves to $< \text{Grade 1}$, then reduce the second cisplatin dose to 80 mg/m^2 .
- If any signs of Grade 3 or greater neurotoxicity occur, discontinue cisplatin but continue radiation.

Renal Adverse Events:

- Cisplatin dose should be based on the serum creatinine or creatinine clearance immediately prior to the second cisplatin dose using the following guidelines: Note: If creatinine is $> 1.5 \text{ mg/dL}$ creatinine clearance must be calculated [Cockcroft-Gault] in order to make dose adjustment. If the calculated creatinine clearance is 50 mL/min or above, a 24-hour urine collection is not needed. If the calculation is $< 50 \text{ mL/min}$, a 24-hour urine collection is mandated, and the cisplatin dose will be determined as follows:

Serum Creatinine		Creatinine Clearance	Cisplatin Dose
$\leq 1.5 \text{ mg/dL}$	or	$> 50 \text{ mL/min}$	100 mg/m^2
$> 1.5 \text{ mg/dL}$	and	$40\text{-}50 \text{ mL/min}$	50 mg/m^2
$> 1.5 \text{ mg/dL}$	and	$< 40 \text{ mL/min}$	Hold drug*

- *Cisplatin should be held but radiation continued and the creatinine measured weekly until it is $< 1.5 \text{ mg/dL}$ or the creatinine clearance is $> 50 \text{ mL/min}$, and then the second dose of cisplatin should be given at the reduced dose of 50 mg/m^2 .

Nausea and Vomiting:

- Maximum supportive therapy will be given and cisplatin will be continued at full dose for $\leq \text{Grade 2}$ nausea and vomiting. For Grade 3 nausea and vomiting refractory to supportive therapy, cisplatin will be held until recovery to $< \text{Grade 2}$. No dose reductions will be made.

Mucositis:

- Significant mucositis of Grade 3 or Grade 4 is expected from radiation, and cisplatin should not be a reason for a treatment break unless it significantly interferes with fluid intake or nutrition. Aggressive supportive care is encouraged.

Ototoxicity:

- For clinical hearing loss not requiring a hearing aid, reduce cisplatin to 50 mg/m^2 . For hearing loss requiring a hearing aid, discontinue cisplatin. For Grade 2-3 tinnitus, at the time of the second dose, hold cisplatin until improvement to Grade 1 or less and then reduce the 2nd dose of cisplatin to 50 mg/m^2 . If tinnitus does not improve to Grade 1 or less by the last day of radiation therapy, discontinue cisplatin.
- An audiogram is strongly recommended when there is any report of significant change in hearing and/or an increase in tinnitus.

For any other grade 3-4 non-hematologic adverse events possibly related to cisplatin, hold cisplatin until toxicities have recovered to grade 1 or less. As noted in Section 5.4.2, in order to assure the maximal immune response to ISA101b, the second 2 doses of ISA101b should each be given at the expected myeloid nadir, i.e. 14 days after administration of cisplatin. This timing should be maintained if the dose of cisplatin is delayed for any reason.

If the second dose of the cisplatin is delayed more than 21 days because of hematologic, neurologic, renal, or other adverse events, that dose will be omitted. If a weight change of $\geq 10\%$ occurs, the second cisplatin dose should be adjusted.

5.5 Intensity Modulated Radiotherapy (IMRT)

5.5.1 Dose specifications

IMRT will be delivered in 35 fractions over 7 weeks (five fractions per non-holiday week) in one plan (SIB). Concomitant boost using separate IMRT plans is not allowed.

Missed treatments due to holidays or logistic reasons can be compensated for by delivering an additional BID treatment during the week, OR treating on the Saturday or Sunday of that week, OR adding to the end of treatment.

5.5.2 Immobilization and Simulation

Patients must have an immobilization device (e.g. Aquaplast mask) made prior to treatment planning CT scan. Use of an immobilizing mouthpiece is strongly encouraged for all patients.

The treatment planning CT scan should be performed with IV contrast so that the major vessels of the neck are easily visualized. The treatment planning CT scan must be performed with the immobilization device and in the treatment position. Slice thickness should be 0.3 cm or thinner.

5.5.3 Target Delineation

The Gross Tumor Volume (GTV) is defined as all known gross disease determined from CT, PET/CT, clinical information, endoscopic findings and/or potentially MRI.

The Clinical Target Volume (CTV) is defined as the GTV plus areas considered to contain potential microscopic disease, delineated by the treating physician. The margin between each GTV and its CTV will typically be a minimum of 0.5 cm except in those areas where the GTV is immediately adjacent to structures known to be uninvolved such as bone and adjacent muscle. In this instance, the CTV should be modified to exclude structures that serve as a boundary that prevents the natural spread of disease (bone, muscle, etc).

The Planning Target Volume (PTV) will provide a margin around each CTV (i.e. both the primary tumor and the lymph nodes containing clinical or radiographic evidence of metastases) to compensate for the variation of treatment set up and internal organ motion. Studies should be implemented by each institution to define the appropriate magnitude of the uncertainty components of the PTV; however, an unedited expansion of 0.3 - 0.5 cm is recommended.

In general, the PTV should not go outside of the skin surface; if it does exceed the skin surface, the application of bolus material over this portion of the PTV may be considered if it is judged clinically that the skin is at risk but is generally not recommended.

For those institutions that are using daily IGRT for margin reduction, the minimum CTV-to-PTV expansion is 3 mm (a larger expansion may be necessary for a target volume subject to significant intra- fraction variability, such

as the non-immobilized oral tongue). In general, the CTV-to-PTV expansion (with IGRT) should not exceed 5 mm.

The primary tumor and involved nodes (CTV1) will typically consist of a 0.5-1.5 cm expansion of the gross tumor volume (GTV) to cover potential local invasion and will be prescribed 2 Gy/fraction, total 70 Gy (see Section 5.5.8. for details of prescription for PTV1).

High-risk sub-clinical disease sites, which include possible local subclinical infiltration at the primary site (primary site CTV2) and first echelon nodes, which are not clinically or radiographically involved (nodal CTV2), should be expanded by 3-5 mm to create PTV2. PTV2 should receive a total dose of 60 Gy/35 fractions.

Lower-risk targets (PTV3) (such as neck nodal levels which are not first echelon nodes and are not adjacent to levels containing grossly involved nodes) will be prescribed 54 Gy/35 fractions.

Treatment of the low neck: see details in Section 5.4.7. If the low neck is treated, the preferred technique is to treat with isocentric matching AP or AP-PA fields with larynx block, matched to the IMRT portals just above the arytenoids. The dose will be 2 Gy per fraction prescribed to 3 cm depth to a total dose of 50 Gy in 25 daily fractions. Whole-neck IMRT is allowed. Involved low neck nodes will receive total 70 Gy in 35 fractions. This can be achieved by either boosting the low neck field with an additional 16 Gy in 8 fractions, by an AP or AP-PA fields, or by planning the whole neck using IMRT. In cases of gross involvement of the vallecula or low neck, whole-neck IMRT should be considered. Whole-neck IMRT may also be considered if level VI is considered to be at risk due to gross involvement of level IV nodes.

All plans must be normalized such that 95% of the volume of the PTV1 is covered with prescription dose of 70 Gy. Additionally: At 1 cc PTV1 volume on the DVH curve, the dose should not be > 110% of the prescribed dose. At a volume of 0.03 cc within the PTV1 volume on the DVH curve, the dose should not be < 95% of the prescribed dose. For any volume of tissue outside the PTVs that has a size of 1 cc, the dose should not be > 74 Gy.

Lymph Node Regions

- a. Submental nodes (*level IA*): In cases where the floor of mouth, oral tongue, or level IB are involved.
- b. Submandibular nodes (*level IB*): To be covered when the ipsilateral level II has nodal disease of at least 3 cm or the oral cavity is involved.
- c. Upper deep jugular (*junctional, parapharyngeal*) nodes: all cases (*at the neck side ipsilateral to the primary tumor*).
- d. Subdigastic (*jugulodigastric*) nodes, midjugular, lower neck, and supraclavicular nodes (*levels II through IV*): all cases, bilaterally; unilateral neck treatment can be considered for well lateralized T1/2 primary tumors.
- e. Posterior cervical nodes (*level V*): all cases, at the neck side where there is evidence of jugular nodal metastases.
- f. Medial retropharyngeal nodes: all cases involving the pharyngeal axis (i.e. not required for oral cavity and larynx cancers not involving pharyngeal structures) should be contoured from the level of C1 through the superior border of the hyoid body.

Critical Normal Structures

The normal tissue volume to be contoured will include the skin surface, brainstem, spinal cord, mandible, glottic larynx, supraglottis, esophagus, trachea, oral cavity, lips, and parotid and submandibular salivary glands. The PRV (planning risk volume) spinal cord contours will be defined at least 0.5 cm larger in the radial dimension than the spinal cord (*i.e. the cord diameter on any given slice will be 1.0 cm larger than the cord itself*). The normal tissues will be contoured and considered as solid organs. The tissue within the skin surface and outside all other critical normal structures and PTVs is designated as unspecified tissue.

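### Low-neck radiotherapy doses do not add up: 50 Gy in 25 plus a 16 Gy in 8 boost is 66 Gy in 33 fractions, not 70 Gy in 35; the ISA101b overdose threshold has a smaller mismatch

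*Combined protocol and SAP*

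**What the plan says.** **Low neck (Section 5.5.3).** For treating the low neck, "the preferred technique is to treat with isocentric matching AP or AP-PA fields". The schedule for that field follows: "The dose will be 2 Gy per fraction prescribed to 3 cm depth to a total dose of 50 Gy in 25 daily fractions". For gross nodal disease in the same region, "Involved low neck nodes will receive total 70 Gy in 35 fractions". Two routes to that total are offered. The first is the boost: "This can be achieved by either boosting the low neck field with an additional 16 Gy in 8 fractions". The second is to plan the whole neck with IMRT. The paragraph adds: "In cases of gross involvement of the vallecula or low neck, whole-neck IMRT should be considered".

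Elsewhere in Section 5.5.3, the primary tumor and involved nodes (CTV1) "will be prescribed 2 Gy/fraction, total 70 Gy", and "All plans must be normalized such that 95% of the volume of the PTV1 is covered with prescription dose of 70 Gy". Lower-risk targets (PTV3) "will be prescribed 54 Gy/35 fractions". Table 8 in Section 5.5.10 lists GTV and CTV70 at 70, and the lower-risk nodal volumes at 50 or 54. Section 5.5.8 sets a cold-spot minimum of 66.5 Gy for PTV70.

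**ISA101b overdose (Section 12.2).** The threshold is 1000 mcg per peptide, described as at least 5 times the indicated dose. Section 5.2.2 fixes the dose at 100 µg/peptide, and Section 5.4.2 allows no adjustment.

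**The concern.** The base schedule, the boost and the total stand in consecutive sentences, and the first two do not sum to the third. This is a delivery instruction for gross nodal disease. A site that follows the written boost gives a nominal dose below the prescription in the sentence before it. A site that follows the prescription must depart from the written boost. The protocol does not say which figure governs.

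The overdose item is smaller. The number and the multiple in Section 12.2 set different cut-offs, so for some doses they disagree on whether an overdose occurred. That decides whether an asymptomatic case is reported as an event of clinical interest, and whether an associated adverse event becomes serious by definition.

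**Working it through.** **Low-neck dose.** All inputs are from Section 5.5.3.

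| Component | Dose | Fractions | Dose per fraction |
|---|---|---|---|
| Matched low-neck field | 50 Gy | 25 | 50/25 = 2 Gy |
| Boost | 16 Gy | 8 | 16/8 = 2 Gy |
| Sum | 50 + 16 = 66 Gy | 25 + 8 = 33 | 66/33 = 2 Gy |
| Stated total | 70 Gy | 35 | 70/35 = 2 Gy |
| Shortfall | 70 − 66 = 4 Gy | 35 − 33 = 2 | 4/2 = 2 Gy |

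The stated total is not reproduced. The sum is 66/70 = 94.3% of it, or 5.7% less. Dose and fraction count are short by the same two 2-Gy fractions. The 66.5 Gy minimum is 0.95 × 70, so a nominal 66 Gy falls 0.5 Gy below it.

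Readings that might reconcile the figures:

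- *Prescription depth.* The base is prescribed at 3 cm and no depth is given for the boost, so the dose at a particular node could differ from 66 Gy. Depth cannot turn 33 fractions into 35.
- *A different base.* Working back from the boost, 70 − 16 = 54 Gy and 35 − 8 = 27 fractions, at 54/27 = 2 Gy each. This adds up, but no 54 Gy in 27 schedule is written. The only 54 Gy schedule is PTV3, over 35 fractions (54/35 = 1.54 Gy each). Adding 8 to that would give 43 fractions.
- *A different boost.* Keeping the written base, 70 − 50 = 20 Gy and 35 − 25 = 10 fractions, at 2 Gy each. This adds up and fits CTV50/PTV50 in Table 8.
- *Another section.* The paragraph points to Section 5.4.7, which does not exist. Section 5.5.7, on low-neck management, describes the match and no-match techniques but gives no doses.

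**ISA101b overdose.**

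- Threshold over dose: 1000/100 = 10 times.
- Five times the dose: 5 × 100 = 500 mcg per peptide.
- The parallel pembrolizumab line is consistent: 1000 mg/200 mg = 5.
- Doses from 500 to below 1000 mcg per peptide are an overdose by the multiple but not by the number.

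**The case against.** The arithmetic is not in dispute. The case on the other side is about consequence.

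- The 70 Gy in 35 prescription is stated clearly and repeatedly: in the low-neck paragraph, in the treatment plan (Section 5), and, for the 70 Gy, under CTV1 and in Table 8. The boost is offered as one permitted means of reaching it. This stands as a reason to treat 70 Gy as the target, but the written means still does not reach it.
- A plan giving 66 Gy to involved nodes would break the 70 Gy coverage rule for PTV1 and the 66.5 Gy minimum, so it should be caught at planning. This stands, and it lowers the chance of harm. The instruction remains wrong.
- The group is narrow. For gross low-neck disease the protocol says to consider whole-neck IMRT, which has no arithmetic problem. The documents give no count of patients on the boost route and no evidence that anyone was underdosed. This stands.
- Changing the boost to 20 Gy in 10 is not proven to be the right repair, because a 54 Gy in 27 base works too. This stands, and radiation oncology must choose.
- The overdose threshold literally satisfies its gloss, since 10 times is at least 5 times, and the explicit number could be read as operative. All adverse events are recorded (Section 12.1), and events serious on other grounds are reported anyway (Section 12.4.1). This stands, and the item is a labelling matter only.

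**Conclusion.** The concern holds. As written, the matched-field-plus-boost route gives a nominal 66 Gy in 33 fractions against a stated 70 Gy in 35: 4 Gy (5.7%) and two fractions short. The dose figure is nominal because the boost depth is not given. The fraction mismatch needs no assumption. The reach is limited to patients with involved low-neck nodes treated by that route, in unknown number, and other planning rules should expose the gap. Because this is a dose for gross disease, it should be fixed.

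The ISA101b threshold is 10 times the trial dose, not 5, which leaves 500 to below 1000 mcg per peptide ambiguous. This is minor.

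Neither item touches sample size, power or the analysis of progression-free survival.

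**What to change.** In Section 5.5.3, do one of the following, with radiation oncology confirming which was intended:

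- change the boost to 20 Gy in 10 fractions, keeping the 50 Gy in 25 base; or
- state a base of 54 Gy in 27 fractions for patients with involved low-neck nodes, and keep the 16 Gy in 8 boost.

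Check the delivered plans of any patient already treated by matched low-neck field plus boost.

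In Section 12.2, set the ISA101b threshold at 500 mcg per peptide with the 5-times label, or keep 1000 mcg and label it 10 times.

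The cost is two corrected figures in an amendment, a short memo to sites and a limited plan check. Design, sample size and analysis do not change.

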5.5.4 Treatment Planning and Delivery

Megavoltage energy photon beam irradiation is required. Any treatment planning and delivery system that has been credentialed for head and neck IMRT for previous RTOG trials is acceptable.

5.5.5 Image Guidance for IGRT When Using Reduced Margins

Daily image guidance of IMRT may be achieved using any one or more of the following techniques:

Orthogonal kilovoltage (KV) images, e.g. ExacTrac;

Linear-accelerator mounted kV and MV helical conebeam CT images;

Linear-accelerator mounted MV CT images (e.g., Tomotherapy);

Other mechanism, after discussion with the Radiation Oncology Co-Chair, [name], PhD.

The institution's procedure for registering daily treatment imaging datasets with a reference dataset should comply with the following recommendations:

Region-of-Interest (ROI) or "clip box" for fusion should be set to encompass the high dose PTV and adjacent spinal cord; if the supraclavicular region is a part of the target volume the ROI should extend to the C6 level; If the fusion software allows the user to create an irregular ROI (e.g., ExacTrac), treatment room objects seen on in-room x-rays should be excluded from the registration; manual (e.g., based on bony anatomy) and automatic (e.g., based on mutual information) types of registration can be used; the result of the fusion must be visually checked for the alignment of the bony anatomy, such as vertebral bodies and applicable soft tissue structures (e.g., optic nerves and/or optic chiasm).

Following the registration, the translational and (if the appropriate technology is available) rotational corrections should be applied to the treatment couch. If all the variances are less than 2.5 mm (this typically corresponds to one half of the usual PRV margin), the treatment can proceed without correction (however, the physician/team may elect to perform adjustments even for a variance < 2.5 mm). If one or more corrections are 2.5-5 mm, adjustment is necessary prior to treatment; however, re-imaging is not mandatory. If one or more of the corrections are larger than 5 mm, the imaging must be repeated in addition to performing table/positioning adjustments. However, the use of numerous repeat IGRT studies should be avoided (see next section).

Management of Radiation Dose to the Patient from IGRT

Estimates of patient doses per imaging study for various imaging systems vary considerably. The doses are in the range of 1 mGy for Cyberknife's and BrainLab's ExacTrac planar kV- systems. The doses from helical MV CT scan on a tomotherapy unit were estimated to be in the range of 1 to 3 cGy for head and neck studies, similar to doses reported for kV cone beam CT on the Elekta Synergy machine. The doses for MV cone beam CT are in the range of 10 cGy for a pelvis study to 6 cGy for a head and neck study. Thus, the doses for 3D imaging systems are in the range from 1 to 6 cGy for head and neck imaging and can contribute from 0.5 to 3% to the daily dose of 2.0 Gy. These dose estimates apply to a single imaging procedure, and the 2 cGy dose is used as a typical fraction size for comparison purposes within the treated region. It is important to point out that the imaging dose typically covers parts of the patient's anatomy that are outside the high-dose region that is treated therapeutically, and that it is sometimes necessary to repeat the procedure a number of times during, before, or after a single fraction delivery. The imaging dose to nearby critical structures may become significant when repeated IGRT procedures are performed for patients with severe set up problems (e.g., requiring frequent corrections of more than 5 mm). It is recommended that patients demonstrating severe set up problems during the first week of treatment be moved to a treatment with larger margins.

5.5.6 Definition of Normal Tissues/Organs at Risk (OARs)

NOTE: Only the parts of the normal tissues/organs at risk outside the PTVs will be considered for dose optimization purposes.

Spinal Cord: The cord begins at the cranial-cervical junction (i.e. the top of the C1 vertebral body). Superior to this is brainstem and inferior to this is cord. The inferior border of the spinal cord is at approximately T3-4

(i.e., just below the lowest slice level that has PTV on it). The spinal cord shall be defined based on the treatment planning CT scan. In addition, however, a Planning Risk Volume (PRV) spinal cord shall be defined. The PRVcord = cord + 5 mm in each dimension. This is irrespective of whether or not IGRT is used.

Brainstem: The inferior most portion of the brainstem is at the cranial-cervical junction where it meets the spinal cord. For the purposes of this study, the superior most portion of the brainstem is approximately at the level of the top of the posterior clinoid. The brainstem shall be defined based on the treatment planning CT scan. In addition, however, a Planning Risk Volume (PRV) brainstem shall be defined. The PRVbrainstem = brainstem + 3 mm in each dimension.

Lips and Oral Cavity: These should be contoured as 2 separate structures as the goal is to keep the lip dose much lower than the oral cavity dose. The definition of lips is self-explanatory. The oral cavity will be defined as a composite structure consisting of the anterior $\frac{1}{2}$ to $\frac{2}{3}$ of the oral tongue/floor of mouth, buccal mucosa, and palate.

Parotid Glands: Parotid glands will be defined based on the treatment planning CT scan.

OARpharynx: This will be defined as the “uninvolved” posterior pharyngeal wall plus adjacent constrictor muscles. This extends from the superior constrictor region (the inferior pterygoid plates level) to the cricopharyngeal inlet (posterior cricoid cartilage level).

Cervical Esophagus: This will be defined as a tubular structure that starts at the bottom of Oropharynx and extends to the thoracic inlet.

Glottic/Supraglottic Larynx (GSL): This will be defined as a “triangular prism shaped” volume that begins just inferior to the hyoid bone and extends to the cricoid cartilage inferiorly and extends from the anterior commissure to include the arytenoids. This includes the infrahyoid but not suprahyoid epiglottis.

Mandible: This includes the entire boney structure of the mandible from TMJ through the symphysis.

Unspecified Tissue Outside the Targets: This will be defined as tissue located between the skull base and thoracic inlet that is not included in either the target volumes or the normal tissues described above.

In cases of weight loss > 10% or significant shrinkage of lymphadenopathy during therapy, it is recommended that the immobilization mask will be adjusted or re-made in order to preserve adequate immobilization, and that a repeated simulation CT be performed to assess the dose distributions in the current anatomy. Whether or not a new IMRT plan will be generated is at the discretion of the treating physician. If a new plan is made, the targets should be the same as those used for the initial plan. The new CT dataset should be used for IGRT image registration when the patient’s shape changes significantly.

